### 13.5.8 Evaluation of ATCH

Exploratory Efficacy Analyses 3.12, 3.13 and 3.14 reflect the analysis of ATCH levels from baseline through 12 weeks of double blind randomized treatment. These Exploratory Efficacy Analyses will be achieved in exactly the same manner as Secondary Efficacy Analyses 2.3, 2.4 and 2.5 described in Sections 13.4.3, 13.4.4 and 13.4.5.

### 13.5.9 Within Subject Correlation of A4 and 17-OHP with tildacerfont Plasma Concentration

Exploratory Efficacy Analysis 3.15 will examine scatter plots of log A4 and log 17-OHP change from baseline values versus corresponding log tildacerfont plasma concentrations over time by tildacerfont dose group and overall. Further, a repeated measures random coefficients mixed-

effects model will be used to estimate the relationship between the change in log A4 (and log 17-OHP) versus the corresponding log tildacerfont plasma concentrations. The model will be a simplified form of the Primary Efficacy Analysis model,

$$y_{ijt} = (\beta_0 + \xi_i) + (\beta_1 + \eta_i)C_{ijt} + \beta_{4j}I_j + \beta_{5j}I_jC_{ijt} + e_{ijt}$$

where:

$y_{ijt}$  is the log A4 change from baseline value for subject  $i, i = 1, \dots, N$ , at time  $t$  in treatment group  $j, j = 1, 2, 3$  (1 = 200mg tildacerfont, 2 = 100mg tildacerfont, 3 = 50mg tildacerfont);  $I_t$  is the indicator for randomised treatment ( $I_t = 1$  for tilacerfont 200mg, =2 for 100mg, =3 for 50mg);  $C_{ijt}$  is the corresponding log tildacerfont plasma concentration,

$\beta_0$  is the fixed intercept effect

$\beta_1$  is the fixed effect of time

$\beta_{4j}$  is the fixed effect of treatment  $j$  parametrized such with  $\beta_{43} = 0$

$\beta_{5j}$  is the effect of treatment  $j$  on time parametrized such that  $\beta_{53} = 0$

$\xi_i$  is the random effect of subject  $i$  intercept

$\eta_i$  is the random effect of subject  $i$  on the linear component of time

$e_{ijt}$  is the random error for subject  $i$  on treatment  $j$  and time  $t$

The intercept and slope values will be extracted from the model for each tildacerfont. The associated fitted regression line will be displayed for each tildacerfont dose, superimposed on top of the individual subject data over time. The y-axis will reflect log A4 (or 17-OHP) change from baseline and the x-axis will reflect log tildacerfont plasma concentration.

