To evaluate the effect of tildacerfont in reducing ATCH in subjects with classic CAH over 12 weeks	3.13.	Absolute change from baseline in ATCH as determined via application of the delta theorem to the log scale analysis results after 12 weeks on double-blind, placebo-controlled treatment (Week 18)
To evaluate the effect of tildacerfont in reducing ATCH in subjects with classic CAH over 12 weeks	3.14.	Change from baseline in ATCH as assessed on the log scale after 12 weeks on double-blind, placebo-controlled treatment (Week 18)

Objective	Efficacy Analysis	
To characterize dose-exposure of Tildacerfont in CAH	3.15.	Estimate the within subject correlation of A4 and 17-OHP log scale values with tildacerfont plasma concentrations over time
Exploratory Efficacy (Optional Open-Label Extension Period) - Outside the Scope of this SAP		
To evaluate the effect of tildacerfont in reducing GC use to near-physiologic levels in subjects with classic CAH	4.1.	Proportion of subjects with GC dose $\leq$ 25 mg/day in HCe and A4 $\leq$ ULN at end of treatment (EOT)
To evaluate the percentage change in GC use in subjects with classic CAH	4.2.	Percent change from baseline in GC dose at EOT
To evaluate the effect of tildacerfont in reducing cardiovascular risk in subjects with classic CAH and at least one cardiovascular risk factor at baseline	4.3.	Proportion of subjects with improvement in at least one cardiovascular risk factor at EOT
To evaluate the effect of tildacerfont in eliminating TART(s) in male classic CAH subjects with TART(s) at baseline	4.4.	Proportion of male subjects without TART(s) at EOT who had TART(s) at baseline
Safety		
To evaluate the safety of tildacerfont in subjects with classic CAH	5.1.	AEs, SAEs

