## **13 EFFICACY ANALYSES**

### **13.1 Primary Efficacy Analysis**

The Primary Efficacy Analysis is planned after all subjects have completed the study Week 18 visit in Part A of the study. During this first 12-week double-blind, placebo-controlled treatment period, there will be no dose escalation. The scheduled visits included in this treatment period include study Week 10, Week 14, and Week 18 corresponding respectively to 4, 8 and 12 weeks of double-blind randomized treatment. Efficacy Analyses will focus on inferences between tildacerfont treated subjects and placebo treated subjects. As shown in [Table 1](#), the Primary Efficacy Analysis (1.1), the five Secondary Efficacy Analyses (2.1, 2.2, 2.3, 2.4 and 2.5), and selected Exploratory Efficacy Analyses (3.1 to 3.6 and 3.15) will be analyzed at the primary analysis. These Efficacy Analyses will be performed using the ITT Analysis Set ([Section 8.2](#)) as the main analyses.

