The random effects,  $\xi_i$ ,  $\eta_i$ , and  $\theta_i$  are assumed independent and identically normally distributed with variance components  $\sigma_\xi^2$ ,  $\sigma_\eta^2$ , and  $\sigma_\theta^2$ , and, independently, the random error  $e_{ij}$  is normally distributed with variance  $\sigma^2$ .

The dose response Primary Efficacy Analysis therefore corresponds to the formal hypothesis statement,

$H_{0L}: \beta_{51} = \beta_{52} = \beta_{53} = 0$  vs  $H_{1L}: \beta_{5j} \neq 0$  for at least one  $j$

and

$H_{0Q}: \beta_{61} = \beta_{62} = \beta_{63} = 0$  vs  $H_{1Q}: \beta_{6j} \neq 0$  for at least one  $j$

The union intersection hypothesis  $H_{0L} \cap H_{0Q}$  represents the null that there is no dose response for tildacerfont versus placebo.

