### **13.5.4 Correlation of Tildacerfont Plasma Concentration vs Dose**

Exploratory Efficacy Analysis 3.4 in [Table 1](#) is the correlation of tildacerfont plasma concentration versus dose. This will be explored by presentation of PK descriptive statistics by dose and scheduled time point (i.e., study Week 10 and 18). Geometric means and geometric mean change from baseline, along with the associated log scale SDs, will be presented.

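### Endpoint 3.15 asks for a within-subject relation to tildacerfont concentration, but the per-dose slopes in SAP 13.5.9 blend within-subject and between-subject relations

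*SAP*

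**What the plan says.** SAP Table 1 defines endpoint 3.15 as: "Estimate the within subject correlation of A4 and 17-OHP log scale values with tildacerfont plasma concentrations over time". Protocol Section 3 words it the same way, and Protocol 9.4.4 gives no method for it. The heading of SAP 13.5.9 also says within subject.

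The method in 13.5.9 is scatter plots, by dose group and overall, plus a model "to estimate the relationship between the change in log A4 (and log 17-OHP) versus the corresponding log tildacerfont plasma concentrations". It has a random intercept and random slope per subject, a dose-group effect, and a dose-by-concentration interaction. The SAP says where this structure comes from: "The model will be a simplified form of the Primary Efficacy Analysis model". The regressor C_ijt "is the corresponding log tildacerfont plasma concentration". It is not centred within subject, and there is no term for the subject's mean. The output is: "The intercept and slope values will be extracted from the model for each tildacerfont" dose, with the fitted line drawn over individual data. Several coefficients are still labelled as effects of time, carried over from the primary model.

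SAP 13.1 sets the timing: "selected Exploratory Efficacy Analyses (3.1 to 3.6 and 3.15) will be analyzed at the primary analysis". That means Part A data, in which dose is fixed. SAP 13.5.4 gives the on-treatment concentration times as "study Week 10 and 18". The schedule of activities takes one PK sample per visit, and the Week 6 sample falls at the baseline visit, after placebo run-in.

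**The concern.** A within-subject relation asks whether the same subject's A4 is lower when that subject's concentration is higher. A between-subject relation asks whether subjects with higher average concentration have lower A4. When a covariate varies at both levels and enters a mixed model once, its fixed slope is a weighted average of the two. A random intercept and random slope do not remove the between-subject part. In the primary model the regressor is time, which takes similar values in every subject, so the issue hardly arises there. Concentration differs between subjects, so replacing time by it creates the problem.

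The design leaves little planned within-subject contrast. The protocol's half-life of about 60 hours puts Week 10 at 28 × 24 / 60 = 11.2 half-lives after the start of randomized dosing, so both samples are close to steady state on one dose. A confounding route is at least plausible. Protocol 4.2 expects that participation may improve GC adherence and shift biomarkers independently of study drug, and SAP 13.3.1 keeps non-compliant subjects in the analysis. A subject who takes both drug and GC reliably could have a higher concentration and lower A4 with no exposure effect. The simplified model also omits the baseline log A4, sex and baseline GC dose covariates of the primary model.

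At stake is the meaning of the reported number: a mixed association would be read as a within-subject one.

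**Working it through.** The documents state no figure for 3.15, so there is none to reproduce. Group size is the plan's 18 per dose.

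**Weight on the between-subject slope.** Take a random-intercept fit with two samples per subject. Let sb and sw be the between- and within-subject SDs of log concentration within a dose, and sξ and se the between-subject and residual SDs of the outcome. Then

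W = sw²/se², B = 2(sb² + sw²/2)/(se² + 2sξ²), weight = B/(B + W).

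All four SDs are assumptions. With sb = 0.5, sξ = 0.5, se = 0.4 and sw = 0.3:
- W = 0.09/0.16 = 0.5625
- B = 2(0.25 + 0.045)/(0.16 + 0.50) = 0.894
- weight = 0.894/1.4565 = 0.61

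Results for sb = 0.5:

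| sw | sξ 0.5, se 0.4 | sξ 0.3, se 0.4 | sξ 0.5, se 0.3 |
|---|---|---|---|
| 0.10 | 0.93 | 0.96 | 0.89 |
| 0.15 | 0.85 | 0.92 | 0.78 |
| 0.30 | 0.61 | 0.76 | 0.50 |
| 0.50 | 0.42 | 0.59 | 0.31 |

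**Size of the per-dose slope when the true within-subject slope is 0.** Assume sξ = 0.45, se = 0.35, sb 0.5 to 0.7, sw 0.25 to 0.4, and 18 subjects. The weight applies to the slope on observed two-sample means, which is itself attenuated by sb²/(sb² + sw²/2).
- Low end (sb 0.5, sw 0.4): W = 0.16/0.1225 = 1.306, B = 0.66/0.5275 = 1.251, weight 0.489, attenuation 0.25/0.33 = 0.758. A between-subject slope of -0.3 gives -0.3 × 0.489 × 0.758 = -0.11.
- High end (sb 0.7, sw 0.25): W = 0.0625/0.1225 = 0.510, B = 1.0425/0.5275 = 1.976, weight 0.795, attenuation 0.49/0.52125 = 0.940. A between-subject slope of -0.5 gives -0.37.

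Simulation of a single dose group, with random intercept and known variances:

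| Between-subject slope | Mean per-dose slope | Nominal 5% rejection |
|---|---|---|
| -0.3 | -0.11 to -0.22 | 12% to 31% |
| -0.5 | -0.18 to -0.36 | 24% to 64% |

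The slope on within-subject deviations averages 0 and rejects in about 5%.

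**Fit of the 13.5.9 model itself.** This used maximum likelihood with random intercept and slope, independent as in the parent model ("are assumed independent and identically normally distributed with variance components"), 3 × 18 subjects, two visits and 400 runs per setting, with sb = 0.5, sξ = 0.5 and se = 0.4. The location of log concentration was set arbitrarily.

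| True within slope | Between slope | sw | Mean slope over doses | Rejection per dose |
|---|---|---|---|---|
| 0 | 0 | 0.15 | -0.006 | 7.7% |
| 0 | -0.5 | 0.15 | -0.40 | 40% |
| 0 | -0.5 | 0.30 | -0.26 | 29% |
| 0 | -0.5 | 0.50 | -0.13 | 16% |
| -0.5 | 0 | 0.15 | -0.09 | 9% |
| -0.5 | 0 | 0.30 | -0.24 | 25% |

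The first row is the background error of the small-sample Wald test. The last two rows show dilution of a real within-subject slope.

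**After splitting concentration.** With true within-subject slope 0 and a between-subject relation, the deviation slope, averaged over doses, has mean -0.05 to +0.02 and rejects in 4.5% to 7.2%. Its SE is 0.375, 0.19 and 0.114 for sw of 0.15, 0.3 and 0.5. Taking the doses as equal and independent, multiplying by √3 gives about 0.65, 0.33 and 0.20 per dose, or 95% half-widths of about 1.3 down to 0.4.

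**The case against.** The strongest reply is that the model is better, and its use more modest, than the concern suggests. Much of this stands.

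- A reader might infer that untransformed concentration is used. It is log concentration; what is missing is centring within subject.
- A reader might infer that differences between doses contaminate the slope. The dose and dose-by-concentration terms remove those. Only differences between subjects on the same dose remain.
- A reader might infer that between-subject differences drive the slope. That depends on variances the documents do not give. With equal SDs of 0.5, the weight is 0.31 to 0.59.
- Rejection rates with doses pooled are higher, but 13.5.9 reports slopes per dose. It also names no test, p-value or interval; SAP 10.5 says only that exploratory endpoints are read nominally at 5%.
- Confounding is not shown. The outcome is change from a baseline averaged over Day 1, Week 4 and Week 6, and subjects below 80% adherence in run-in are excluded. The between-subject slopes used above are assumptions.
- A reader might infer that a false exposure-response line would feed into dose choice. Protocol 4.2 and 4.3 state a general exposure-response aim, but no passage ties 13.5.9 to dose selection. Dose response is tested by the primary model, and SAP Section 4 sends cross-study dose-exposure-response work to a separate plan.

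Relabelling the slope as a mixed association would be a cheaper remedy. It would cure the mislabelling but leave 3.15 unanswered. None of these points makes the uncentred slope a within-subject quantity, and the separate PK plan does not replace 13.5.9.

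**Conclusion.** The concern holds as a mismatch between endpoint and estimator. Endpoint 3.15 is a within-subject quantity, and nothing 13.5.9 extracts is one. The reported slope can be non-zero with no within-subject relation, or be diluted when one exists. A false slope requires a between-subject relation on the same dose; with none at either level, the slope averages close to 0. The sizes rest wholly on assumed variances and slopes, and they illustrate what can happen rather than predict this trial. Severity is low: the analysis is exploratory and nominal, and no primary or secondary result changes.

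**What to change.** In SAP 13.5.9:

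- Replace C_ijt by two terms: each subject's mean log concentration over the Part A on-treatment samples, and each sample's deviation from that mean.
- Add visit as a fixed effect. Protocol 4.2 reports that response strengthened over 12 weeks in an earlier study, so a time trend could pass for a concentration effect.
- Report the deviation slope, with its confidence interval, as endpoint 3.15. Report the mean slope separately, labelled as a between-subject association. Do the same for 17-OHP.
- Correct the coefficient labels that still refer to time.

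The cost is a few sentences, the derived mean and deviation, and no new data. The downside is precision: a per-dose SE of roughly 0.2 to 0.65 under the assumed variances. Subjects with only one on-treatment sample add nothing to the deviation slope, and the random slope is weakly identified with two samples. Adherence that changes between Weeks 10 and 18 can still confound the deviation slope, and the text should say so.

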### 13.5.10 Additional Exploratory Analyses

#### 13.5.10.1 Menstrual Cycle Length

Menstrual cycle length, which is defined in [Section 9.3.27.1](#), will be summarized descriptively by treatment group and scheduled time point. The time between menstrual cycles, which is defined in [Section 9.3.27.2](#), will also be summarized descriptively.

### **13.5.10.2 Number of Stress Dosing Events**

A stress dosing event is derived from the daily GC diary. The number of stress dosing events ([Section 9.3.26.4](#)), number and proportions (expressed as percentages) of subjects who underwent stress dosing, along with their exact (Clopper-Pearson) 95% CIs, will be summarized by treatment period (Parts A, B, and C) and scheduled time point.

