4.1.3 Study Diary/Drug Adherence Data Collection

Subjects will be asked to maintain an electronic study diary to capture daily information during the Run-in and Treatment Periods. The Investigator is responsible for ensuring that subjects record the appropriate information in their diaries. Subjects will document study drug and background GC adherence through Week 18. Female subjects will also use the study diary to record menstrual information (including start and stop dates of menses) across the full treatment period up to Week 76.

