6.5.1.5 Stress Dosing of Glucocorticoid

During times of clinically significant physical stress such as intercurrent illness with fever, surgical procedures, or significant trauma, subjects may take extra GC (in the form of HC) consistent with the "sick day guidelines" for prevention of adrenal crisis shown in [Table 2 \(Bornstein 2016\)](#). Sites may employ variations on these guidelines, consulting with the Medical Monitor, if possible, in non-urgent situations. The Sponsor will provide all subjects with oral HC for the purposes of stress dosing ([Section 6.2.2](#)). For subjects who are not taking HC as their background GC regimen, the stress dose of HC should be estimated based on the relative potencies of GCs outlined in [Table 1](#).

The stress doses recommended in [Table 2](#) are meant to *replace* a subject's usual daily GC dose; they are NOT taken *in addition* to the subject's usual daily GC dose. When taking the stress dose orally, the subject should take the entire stress dose using HC tablets from the bottle provided by the Sponsor. The subject's physician-prescribed GCs should be temporarily held during stress dosing and reinstated as soon as the stress dosing period ends.

While all GC stress doses should be entered into the EDC, changes to usual daily GC dose only need to be entered into EDC when there is a definitive long-term, chronic alteration in the usual daily GC dosing regimen.

Table 2. Sick Day Guidelines for Stress Dosing of Hydrocortisone

Condition	Stress Dosing of Hydrocortisone
Home management of fever >38 °C (>100.4 °F) or illness requiring bed rest, when requiring antibiotics for an infection, or before undergoing a minor outpatient procedure (eg, dental work)	
Approximately double the routine oral GC dose (and give as HC) until recovery (usually 2 to 3 days)For fever >39 °C (102.2 °F) only, approximately triple the routine oral GC dose (and give as HC) until recovery (usually 2 to 3 days)¹Increase consumption of electrolyte-containing fluids and simple and complex carbohydrates (El-Maouche 2018), as tolerated
Unable to tolerate oral medication due to gastroenteritis or trauma	
HC 100 mg IM or SC
Minor to moderate surgical stress	
HC 25 to 75 mg/24 hours (usually 1 to 2 days)

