### 9.3.23.7 Diary Compliance

Subjects will fill out the daily GC and study drug diary through the Run-in Period and Part A. For all diary compliance, missing entries are counted as non-compliance. Daily study drug diary

compliance is calculated as the total count of number of 'Yes' responses to taking study drug as directed divided by (LASTDAY – FIRSTDAY+ 1 day), where LASTDAY is the date of last dose, and FIRSTDAY is the date of first dose.

Daily food diary compliance is calculated as the total count of number of 'Yes', with evening meal' responses to taking study drug with an evening meal, divided by (LASTDAY – FIRSTDAY+ 1 day).

Daily GC diary compliance is calculated as the total count of number of 'Yes' or 'Took Stress Dosing' responses to taking GC as directed and number of stress dosing days, divided by (LASTDAY – FIRSTDAY+ 1 day).

Weekly diary compliance is calculated as the total count of number of 'Yes', 'Yes, with evening meal' and/or 'Took Stress Dosing' responses to taking study drug as directed within the duration {Study Day (7n+1) to Study Day (7[n+1])}, divided by 7. Where n has values {0, 1, 2, ..., 18}. Missing entries are counted as non-compliance.

Aggregate diary compliance is calculated as (study drug compliance + food compliance + GC diary compliance) divided by 3.

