### 9.3.26.3 Stress Event

A stress event is defined as an entry in the diary indicating a stress dose was taken. Consecutive days of stress dosing are counted as a single stress event.

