 Subjects will use an electronic study diary to document study drug and background GC adherence through Week 18. Female subjects will also use the study diary to record menstrual information (including start and stop dates of menses) across the full treatment period up to Week 76.

 A full physical examination will be conducted at Day 1, Week 18, and Week 76. The full physical examination may exclude rectal, genitourinary, and breast exams. An abbreviated physical examination will be conducted at all other visits indicated. If the physical exam is performed at the subject's home, the qualified medical professional will report any changes to the subject's health to the site to determine whether further evaluation is needed via an unscheduled visit.

 At Week 6, acne will be evaluated in all subjects and hirsutism in all female subjects. After Week 6, acne/hirsutism will only be evaluated in subjects who had acne/hirsutism at Week 6.

17-OHP = 17-hydroxyprogesterone; A4 = androstenedione; ACTH = adrenocorticotrophic hormone; AE = adverse event; ALP = alkaline phosphatase; ALT = alanine aminotransferase; AST = aspartate aminotransferase; CGI-I = Clinical Global Impression – Improvement Scale; C-SSRS = Columbia–Suicide Severity Rating Scale; EC = Ethics Committee; ECG = electrocardiogram; EDC = electronic data capture; ET = early termination; FCP = female of childbearing potential; FSH = follicle-stimulating hormone; GC = glucocorticoid; GGT = gamma-glutamyl transferase; HADS = Hospital Anxiety and Depression Scale; HbA1c = hemoglobin A1c; HC(e) = hydrocortisone (equivalents); HIV = human immunodeficiency virus; HOMA-IR = homeostatic model assessment of insulin resistance; IGA = Investigator's Global Assessment (score for acne); INR = international normalized ratio; IRB = Institutional Review Board; LH = luteinizing hormone; mFG = modified Ferriman-Gallwey (score for hirsutism); PGIC = Patient Global Impression of Change; PK = pharmacokinetics; PRN = as needed; PROs = patient-reported outcome measures; PT = prothrombin time; PTT = partial thromboplastin time; RTSM = randomization and trial supply management (system); SF-36 = Short Form 36; SHBG = sex hormone-binding globulin; T = telephone contact; TART = testicular adrenal rest tumor; V = study visit.

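### Stress-dosing events are to be summarised for Parts A, B and C, but the daily GC diary they are derived from ends at Week 18

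*SAP*

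**What the plan says.** **Event source.** SAP 13.5.10.2 states: "A stress dosing event is derived from the daily GC diary". SAP 9.3.26.3 gives the only definition: "A stress event is defined as an entry in the diary indicating a stress dose was taken". Consecutive days count as one event.

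**Periods reported.** Under SAP 13.5.10.2 the results "will be summarized by treatment period (Parts A, B, and C) and scheduled time point". SAP 12.2 also calls for the proportion of subjects with an event, the number of events and their duration, overall and in each of the three parts.

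**Diary coverage.** SAP 9.3.23.7: "Subjects will fill out the daily GC and study drug diary through the Run-in Period and Part A". Protocol 4.1.3: "Subjects will document study drug and background GC adherence through Week 18". Protocol 6.4 and the footnotes to both post-screening schedules agree; the SAP's Table 14 reads "Subjects will use an electronic study diary to document study drug and background GC adherence through Week 18". Only menstrual entries by female subjects run on to Week 76.

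**Other records.** Protocol 6.5.1.5 begins a sentence on data entry with "While all GC stress doses should be entered into the EDC" and sets no end week. Protocol 8.3.8 places the start and stop dates and the cause of each stress-dosing episode in the patient diary, also with no end week.

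**The concern.** The plan names a data source for one period and asks it to describe three. Stress dosing is allowed throughout the study (Protocol 6.5.1.1), and sponsor-supplied hydrocortisone is dispensed and accounted for through Week 76, so episodes are expected after Part A.

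Part C is where subjects with A4 at or below the ULN begin to lower their GC dose. How often they needed stress doses then is useful context for any GC-sparing claim. A table that fills in for Part A and then goes blank or to zero could be taken as a finding about the drug when it only reflects when the diary closed.

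**Working it through.** **1. Calendar.** The visit schedule puts Part A at Weeks 6 to 18, Part B at Weeks 18 to 30 and Part C at Weeks 30 to 76.

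- Lengths: 18 − 6 = 12, 30 − 18 = 12, 76 − 30 = 46. The sum is 70, which reproduces the stated Treatment Period.
- Covered by the daily GC diary: 12/70 = 17%.
- Not covered: (12 + 46)/70 = 58/70 = 83%. By target study day: (84 + 322)/490 = 406/490 = 83%.
- GC reduction in the main study follows the Week 38 and Week 46 visits, so all of it lies in the uncovered part.

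The 83% is a share of calendar time. It is not a share of events, for which the documents give no rate.

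**2. The SAP's own last diary week.** The weekly compliance formula in SAP 9.3.23.7 covers Study Days 7n + 1 to 7(n + 1): "Where n has values {0, 1, 2, ..., 18" and no further. The last week therefore runs from Study Day 127 to 7 × 19 = 133. The Week 18 target is Day 127 and the Week 76 target is Day 533. Even on this reading the diary reaches at most one week into Part B.

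**3. Where the stress entry sits.** In SAP 9.3.23.7, having taken a stress dose is one of the responses counted in daily GC diary compliance. It belongs to the adherence record that closes at Week 18. SAP 9.3.26.2 leaves stress doses out of the derived total daily GC dose, so that variable cannot fill the gap.

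**4. What the table would print if a missing entry counts as no event.** For zero events in n subjects, the exact upper 95% limit is 1 − 0.025^(1/n). The lower limit is 0.

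- All 72 planned subjects: 1 − 0.025^(1/72) = 5.0%.
- One planned group of 18: 1 − 0.025^(1/18) = 18.5%.

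Either would look like an estimate although nothing had been recorded.

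**5. Illustration under assumed rates.** The rates below are assumptions, not figures from the documents. They suppose 72 subjects followed throughout at a constant rate r per subject-year. Expected events = 72 × r × weeks × 7/365.25.

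| Assumed r | Part A | Part B | Part C |
|---|---|---|---|
| 0.5 | 8 | 8 | 32 |
| 1 | 17 | 17 | 63 |
| 2 | 33 | 33 | 127 |

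A source limited to the daily diary would miss essentially all events in the last two columns.

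**6. Cross-references.** SAP 13.5.10.2 and 12.2 both send the reader to 9.3.26.4 for the event. That section defines baseline GC dose; the stress event is in 9.3.26.3. SAP Section 15 does not mention any of this.

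**The case against.** The best counter-evidence is Protocol 8.3.8, which has subjects record stress-episode details in the diary and sets no Week 18 limit. Protocol 4.1.3 describes the diary as covering the Run-in and Treatment Periods, and its Week 18 limit names study drug and background GC adherence, not stress episodes. Both schedules also mark diary review through Week 76, although the menstrual entries may explain that. Diary entries for stress episodes may therefore continue after Week 18. This stands and makes the conclusion conditional. It does not remove the conflict, because SAP 13.5.10.2 specifies the daily GC diary and SAP 9.3.23.7 closes that diary at Part A.

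SAP 12.2 names an eCRF as the source of GC dosing. That is true, but its event count still points back to the 9.3.26 definitions, so it gives no separate source for stress events.

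A careful programmer might show Parts B and C as not collected. The SAP neither says so nor says the opposite. With that display there would be a gap, not a false zero.

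A reader might go further and infer that the plan will make tildacerfont appear to reduce adrenal crises. The documents do not support that:

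- Protocol 7.1.5 and 8.3.8 treat stress dosing as prevention, not as adrenal insufficiency.
- Adrenal insufficiency has its own form, and events that trigger stress dosing go on the adverse event form.
- SAP 14.1 summarises adverse events separately for each part.
- Parts B and C have no placebo arm, so no randomised comparison is biased.

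A reader might also assume that the EDC already holds complete, dated stress episodes. Protocol 6.5.1.5 requires the entries but describes no fields. The only text that assigns start and stop dates to episodes is Protocol 8.3.8, and it puts them in the diary.

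**Conclusion.** The mismatch between source and reporting period is real and appears in the text of both documents. As written, the SAP has no daily GC diary source for essentially all of the 58 weeks of Parts B and C.

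The result is an empty summary for those parts if no stress-episode diary entries are made after Week 18. It becomes a misleading zero only if, in addition, a missing entry is counted as no event. SAP Section 4 lets SAP wording govern where it and the protocol disagree on planned analyses, so the protocol's EDC requirement does not by itself correct the derivation.

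The reach is limited. The item is listed among additional exploratory analyses, is not an endpoint in SAP Table 1, and leaves the primary and secondary analyses untouched. It should be corrected because it concerns the GC-reduction phase and the remedy is small.

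**What to change.** 1. In SAP 9.3.26.3 and 13.5.10.2, derive stress-dosing events in all three parts from the stress-dose entries that Protocol 6.5.1.5 requires in the EDC, together with any episode records kept under Protocol 8.3.8. Use the daily GC diary as a cross-check through Week 18. Apply the same source in SAP 12.2.
2. First confirm that those records carry what is needed to define an event and its duration. If they do not, restrict the diary-based summary to Part A and show Parts B and C as not collected, never as zero.
3. Reconcile SAP 9.3.23.7 with Protocol 4.1.3, 6.5.1.5 and 8.3.8 on whether stress episodes are entered in the diary after Week 18.
4. Change the cross-reference from 9.3.26.4 to 9.3.26.3 in SAP 13.5.10.2 and 12.2.

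The cost is SAP derivation wording and a check of the EDC stress-dose form. No new data collection is needed if the required entries hold usable dates. If they do not, the cost is losing the Part B and C summary, to be stated openly.
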